#### 10.4.5 ANALYSIS OF SECONDARY EFFECTIVENESS ENDPOINTS

Participants will undergo cognitive testing with both the DCTclock and the reference standard, MMSE twice, where the second examination will be one to four weeks after the first examination. The secondary endpoints are DCTclock scores, MMSE scores and assessment of DCTclock and MMSE impaired and unimpaired status at each of two time points. The secondary analysis will assess the comparability of DCTclock test-retest reliability to that of MMSE. DCTclock test results of “unanalyzable” will be excluded from these analyses. Also, participants who no longer satisfy the inclusion/exclusion criteria prior to the second examination will also be excluded from this analysis.

Agreement analysis: For each of DCTclock and MMSE separately, the agreement between the first and second measurements will be carried out as follows:

1. A scatter plot of reading 2 vs. reading 1 will be generated, superimposed with a line of identity. An unweighted Deming regression (where the variance of the measurement error for each of DCTclock and MMSE is determined by the two measurements that were collected 1-4 weeks apart) will be carried out to determine the y-intercept, slope and their two-sided 95% confidence intervals. The correlation coefficient will also be determined. A hypothesis test of the slope vs. 1 and of the y-intercept vs. 0 will be carried out. Specifically, the following hypothesis test will be carried out:

$$H_0: \beta_0 = 0 \text{ vs. } H_1: \beta_0 \neq 0 \quad \text{and} \quad H_0: \beta_1 = 1 \text{ vs. } H_1: \beta_1 \neq 1$$

where  $\beta_0$  and  $\beta_1$  are the y-intercept and slope, respectively, from the Deming unweighted regression.

2. Within each of DCTclock and MMSE separately, participants will be categorized as impaired, not impaired or indeterminate/intermediate for each of the two measurements obtained on each participant. A 3-by-3 table, with the rows being the second reading status and with columns being the first reading cognitive status, will be generated as follows for each of DCTclock and MMSE:

		Reading 1			
Reading 2		Impaired	Indeterminate/Intermediate	Unimpaired	Total
	Impaired	a	b	c	a+b+c
	Indeterminate/intermediate	d	e	f	d+e+f
	Unimpaired	g	h	i	g+h+i
	Total	a+d+g	b+e+h	c+f+i	a+b+c+d+e+f+g+h+i

The following statistics will be calculated from the above table:

Positive Percent Agreement (PPA):  $a/(a+d+g)*100$  and its two-sided 95% Wilson confidence interval

Negative Percent Agreement (NPA):  $(e+f+h+i)/(b+c+e+f+h+i)*100$  and its two-sided 95% Wilson confidence interval.

A quadratic weighted kappa score will be generated along with its Wald two-sided 95% confidence interval. This analysis will be repeated with the indeterminate/intermediate groups omitted.

Percent agreement for impaired:  $a/(a+d+g)*100$  and its two-sided 95% Wilson confidence interval.

Percent agreement for indeterminate/intermediate:  $e/(b+e+h)*100$  and its two-sided 95% Wilson confidence interval.

Percent agreement for unimpaired:  $i/(c+f+i)*100$  and its two-sided 95% Wilson confidence interval.

3. Within each of DCTclock and MMSE separately, participants will be categorized as impaired, not impaired or indeterminate/intermediate at each of the two measurements obtained on each participant. A 3-by-3 table, with the rows being the second reading status and with columns being the first reading cognitive status, will be generated as follows for each of DCTclock and MMSE:

		Reading 1			
Reading 2		Impaired	Indeterminate/ Intermediate	Unimpaired	Total
	Impaired	a	b	c	a+b+c
	Indeterminate/ Intermediate	d	e	f	d+e+f
	Unimpaired	g	h	i	g+h+i
	Total	a+d+g	b+e+h	c+f+i	a+b+c+d+ e+f+g+h+i

The Fisher-Freeman-Halton exact test will be used to assess if the cognitive classifications differ between reading 1 and 2 for each of DCTclock and MMSE. The null hypothesis is that reading 2 and reading 1 do not differ with respect to cognitive classifications.

4. If results show a significant difference between test and retest for DCTclock, that does not imply that DCTclock is less reliable than MMSE or other neuropsychological tests. The intraclass correlation for each of DCTclock test-retest difference, the MMSE test-retest difference, and neuropsychology battery variables' test-retest differences will be calculated. The test-retest weighted kappa statistic for determination of impaired status will also be calculated for DCTclock and MMSE. Results showing that DCTclock has similar or better ICC/ kappa than neuropsychological battery variables and MMSE will be considered as sufficient reliability of DCTclock.

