### 10.3 ANALYSIS DATASETS

- Intention-to-Treat (ITT) Analysis Dataset: all enrolled participants
- Evaluable Analysis Dataset: all enrolled participants undergoing cognitive testing with both DCTclock and MMSE and who are not performing suboptimally (as determined by the Reliable Digit Score). This is the primary analysis set for effectiveness.
- Safety Analysis Dataset: all enrolled participants undergoing cognitive testing with DCTclock. This is the primary analysis set for safety.

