### 10.4 DESCRIPTION OF STATISTICAL METHODS

#### 10.4.1 GENERAL APPROACH

All subjects will undergo testing with DCTclock, MMSE, and MoCA. A non-inferiority analysis using a two-sided tests (TOST) approach will be conducted comparing the quadratic weighted kappa between DCTclock and MoCA to the quadratic weighted kappa between MMSE and MoCA.

The remaining analysis comparing DCTclock to MMSE will be descriptive, providing two-sided 95% confidence intervals of important parameters when necessary.

Descriptive statistics include sample size, mean, standard deviation, median and quartiles for continuous variables, and counts and percents for categorical variables. All confidence intervals will be two-sided 95% confidence intervals, and all p-values will be two-sided, using a two-sided 0.05 level of significance. There will be no imputation of missing data. Statistical analysis will be conducted with R version 3.4 or higher.

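### Unanalyzable DCTclock results leave the test-retest analysis with no common set of complete pairs, so the DCTclock and MMSE reliabilities compared in item 4 of Section 10.4.5 can rest on different participants (minor, cheap to fix).

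*Protocol*

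**What the plan says.** Protocol Section 10.4.5 covers test-retest reliability, with the second examination one to four weeks after the first. It sets two exclusions in consecutive sentences. The first concerns results of one test: "DCTclock test results of “unanalyzable” will be excluded from these analyses". The second concerns people: "participants who no longer satisfy the inclusion/exclusion criteria prior to the second examination will also be excluded from this analysis". The analyses are then run test by test: "For each of DCTclock and MMSE separately, the agreement between the first and second measurements will be carried out as follows".

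Item 4 of the section brings the two tests back together. It calculates ICCs for DCTclock, MMSE and the battery variables, and adds kappa: "The test-retest weighted kappa statistic for determination of impaired status will also be calculated for DCTclock and MMSE". The conclusion follows from a comparison: "Results showing that DCTclock has similar or better ICC/ kappa than neuropsychological battery variables and MMSE will be considered as sufficient reliability of DCTclock".

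Two other places bear on who is included. Section 10.3 defines the Evaluable set as "all enrolled participants undergoing cognitive testing with both DCTclock and MMSE and who are not performing suboptimally". Section 10.4.1 states "There will be no imputation of missing data".

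**The concern.** A comparison of two reliabilities is clean only if both are estimated on the same people. ICC and kappa depend on the spread of scores in the sample as well as on measurement error. Removing some people from one test and not the other can therefore move the comparison even when the tests are equally reliable.

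The bias could go either way. If a bad session spoils both tests, the exclusion cleans DCTclock and leaves the damage in MMSE, which flatters DCTclock. If the weakest performers produce the unanalyzable drawings, DCTclock loses the low end of its range and looks worse. Item 4 gives no numerical margin for 'similar', so a small artificial gap could influence the judgement.

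**Working it through.** **Reading the text.**
1. The first exclusion names results of DCTclock. The second names participants, and so applies to both tests.
2. The agreement analyses are run separately for each test.
3. Membership of the Evaluable set requires having undergone both tests. A person with an unanalyzable drawing has done so and stays in. The definition does not ask for an analyzable result or for two complete pairs.
4. With no imputation, that person contributes no DCTclock pair but can contribute an MMSE pair.
5. Item 4 compares the two estimates and does not restrict the participants.

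There is no figure of the plan's own to reproduce here.

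**Size: inputs.** From the protocol: 400 evaluable participants, and an indeterminate share between 15% and 60% (Section 10.4.3). Assumed: test-retest correlation 0.80 for both tests, so the true gap is zero; true-score correlation between the tests 0.5 to 0.7; category splits 20/60/20 and 42.5/15/42.5; and 2%, 5% or 10% of DCTclock retests unanalyzable (8, 20 or 40 of 400).

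**Formulas.** Quadratic weighted kappa = 1 − Σw·p(observed)/Σw·p(expected), with w = ((i−j)/2)². One-way ICC = (MSB − MSW)/(MSB + MSW). With nothing excluded, kappa is 0.64 (20/60/20) or 0.66 (42.5/15/42.5), and the ICC is 0.80.

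**Scenario (a): a bad retest session turns both readings into noise.** If a share u of retests is independent noise with unchanged margins, MMSE kappa becomes (1 − u) × kappa, while DCTclock, with those cases removed, keeps kappa. The gap is u × kappa:
- 2%: 0.02 × 0.64 = 0.013
- 5%: 0.05 × 0.64 = 0.032, or 0.05 × 0.66 = 0.033
- 10%: 0.10 × 0.64 = 0.064, or 0.10 × 0.66 = 0.066

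The ICC gap is u × 0.80: 0.016, 0.04 and 0.08. Simulation with 2,000,000 draws agrees.

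**Scenario (b): the lowest DCTclock retest scorers are unanalyzable.** Taken from the same simulation.

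| Unanalyzable retests | Failures unrelated to performance | (a) kappa gap as written | (b) kappa gap as written |
|---|---|---|---|
| 2% | 0.00 | about +0.01 | -0.01 to -0.02 |
| 5% | 0.00 | about +0.03 | -0.02 to -0.04 |
| 10% | 0.00 | +0.06 to +0.07 | -0.05 to -0.08 |

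The ICC gap in (b) is about -0.03 at 5% and -0.055 at 10%.

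**With the same participants for both tests.** In (a) the gap returns to 0.00. In (b) it shrinks but remains: kappa about -0.01 to -0.035 at 5% and -0.025 to -0.07 at 10%.

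**Scenario (c): the noise is in DCTclock only.** The exclusion raises DCTclock's own kappa by about 0.03 at 5% and 0.06 to 0.07 at 10%. A common set does not change this.

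**A second design** (30/40/30 split, failures possible at either visit, 5% per test) also gave both directions. With failures tied to underlying ability, DCTclock ICC was 0.758 to 0.771 against MMSE 0.800. With the excluded people measured at twice the error SD on both tests, it was 0.799 against 0.776. On a common set the two tests agreed to within 0.002.

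**Against sampling error.** The standard error of the kappa gap at n = 400 is 0.04 to 0.05 (simulated), so the 5% bias is at most about one standard error.

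**The case against.** The exclusion can be read as joint. It follows directly on a sentence that defines the analysis as a comparison of the two tests, and the next sentence adds a further exclusion with 'also'. On that reading the person leaves both tests and nothing is wrong. This stands as a possible reading, but the change from results to participants means the text does not establish it. Which pairs enter a descriptive comparison is also often settled in an SAP, and Section 10.1 promises one. Here, though, the protocol itself fixes both the exclusion and the comparative rule.

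Existing safeguards cover part of scenario (a). Visit 2 repeats the screens (Section 7.3.2), and a participant who fails one does not go on. The pegboard comes after DCTclock and before MMSE, so some shared bad sessions already yield no second MMSE. The Evaluable set also removes suboptimal performers for both tests.

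Scenario (a) is an upper case too, because it assumes that every failed drawing comes with a ruined MMSE. If only half do, the 5% gap falls to about 0.05 × 0.5 × 0.64 = 0.016. In scenario (b), the text as written penalises DCTclock and so is conservative. All of this stands, and it is why the point is minor.

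A reader might infer that the exclusion favours the device, or that it undermines the reliability claim. The documents do not support either: they give no failure rate or cause, the direction of any bias is open, and failures unrelated to performance give none.

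**Conclusion.** The point holds as a cheap improvement. Followed literally, Section 10.4.5 allows the two reliabilities in item 4 to be estimated on different participants, and no other section prevents it. The bias is zero if failures are unrelated to performance. Otherwise it is a few hundredths of kappa at an assumed 5% rate, in an unknown direction, and within about one standard error. It would exceed that only at rates nearer 10%.

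These sizes rest on assumed correlations, failure rates and failure mechanisms. The comparison is secondary and described as descriptive in Section 10. The primary analysis uses first-examination scores only (Section 10.4.2) and is not touched by this exclusion.

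**What to change.** In Section 10.4.5:
- State that the item 4 comparison of DCTclock with MMSE uses participants with two analyzable DCTclock readings and two MMSE readings. Compute the ICC and the full three-by-three quadratic weighted kappa of both tests on that set.
- For each battery test, compare on participants with complete pairs on both DCTclock and that test. The asterisked tests exist only for participants who completed visit 1 under protocol version 1 (Section 7.3.4), so a single common set would not serve.
- Show MMSE reliability on all available participants as a sensitivity result.
- Report the number and share of unanalyzable DCTclock results by visit. This is needed because a common set only partly corrects selective failure and does not correct noise confined to DCTclock.

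The cost is a few sentences and a few table lines, with no new data. The MMSE set for this comparison becomes slightly smaller: 20 fewer of 400 if 5% of retests fail, or up to 400 × (1 − 0.95²) = 39 if 5% fail independently at each visit.

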## SCHEMATIC OF STUDY DESIGN

1. Subject recruitment.
2. Those subjects who meet the inclusion criteria will be consented (Administrator #1).
3. Screening tests and the DCTclock test will be administered (Administrator #1).
  - a. Screen for impairment of dominant hand
  - b. Screen for drug/alcohol use
  - c. Reading and comprehension assessment
  - d. Hamilton-Veale Contrast Sensitivity [1]
  - e. DCTclock
  - f. Purdue Peg Board [2]
4. The Neuropsychological test battery and questionnaire will be administered (Administrator #2).
  - a. MMSEworld [3]
  - b. MoCA [4]
  - c. Benton Judgement of Line Orientation [5]\*
  - d. Rey Complex Figure [6]\*
  - e. Delis-Kaplan Executive Function System (D-KEFs) Verbal Fluency (sub-test of D-KEFs) [7]\*

- f. Digit Span and Reliable Digit Calculation (sub-test of Wechsler Adult Intelligence Scale-WAIS-IV) [8]
  - g. Block Designs (sub-test of WAIS-IV) [8]\*
  - h. Trail Making Test – Parts A and B [9]
  - i. Symbol Digit Modalities [10]\*
  - j. Geriatric Depression Scale (15 item version). [11]\*
5. Repeat steps 3 and 4 (above) in the same subjects after one to four weeks without feedback, minimizing learning effects.

Assessments indicated with an asterisk (\*) above will only be given to participants who complete visit 1 under protocol version 1.

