### 5.4.2 HANDLING OF PARTICIPANT WITHDRAWALS OR TERMINATION

Participants who withdraw or terminate from the study will not be pursued as the study has no follow-up or long term safety and effectiveness endpoints. Participants who withdraw or do not complete the second visit will not be replaced as the overall sample size will take into account potential withdrawals.

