### 10.4.3 SAMPLE SIZE

Approximately 500 participants will be enrolled to obtain 400 evaluable participants. The evaluable sample size is the same as the evaluable sample size used in “De Novo Classification Request for Cognivue”. The primary null and alternative hypotheses are:

$$H_0: \kappa \leq 0.40 \quad \text{vs.} \quad H_1: \kappa > 0.40$$

where  $\kappa$  is the quadratic weighted kappa statistic calculated from the above DCT-MMSE classification table. Power for quadratic weighted kappa requires assumptions of the values on the diagonal and off-diagonal of the table, which is a large number of assumptions. Power will thus be calculated for the unweighted kappa which requires fewer assumptions. It is assumed that the quadratic weighted kappa will be similar to or larger in magnitude than the unweighted kappa and with similar standard error as the unweighted kappa, so the study will be powered to show that the unweighted kappa  $> 0.4$  with the expectation it will then be sufficiently powered to show that the quadratic weighted kappa  $> 0.4$ . An evaluable sample size of 400 subjects yields at least 80% power to reject the above null hypothesis at one-sided 0.025 level of significance under the assumptions that: (1) the true kappa is 0.52 or more; (2) the marginal percentage of participants categorized as impaired is between 20% and 42.5% for DCTclock; (3) the marginal percentage of participants categorized as impaired for MMSE is the same as that for DCTclock; (4) the marginal percentage of participants categorized as unimpaired for DCTclock is the same as the marginal percentage of participants categorized as impaired for DCTclock; (5) the marginal percentage of participants categorized as unimpaired for MMSE is the same as that for DCTclock; and (6) the marginal percentage of participants categorized as indeterminate is between 15% and 60% for each of DCTclock and MMSE and is equivalent between DCTclock and MMSE.

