#### 10.4.11 MULTIPLE COMPARISON/MULTIPLICITY

Given the nature of the analysis, there will be no adjustment for multiple comparisons.

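### Section 10.4.5 item 1 tests test-retest change through the Deming intercept at score 0, so its power for a uniform shift depends on where zero lies on the scale; the paired mean difference does not have this problem

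*Protocol*

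**What the plan says.** Protocol section 10.4.5 item 1 plots reading 2 against reading 1 with the identity line. It then fits an unweighted Deming regression in which "the variance of the measurement error for each of DCTclock and MMSE is determined by the two measurements that were collected 1-4 weeks apart". Intercept, slope, their 95% confidence intervals and a correlation are reported, and "A hypothesis test of the slope vs. 1 and of the y-intercept vs. 0 will be carried out". Two null/alternative pairs follow, one for each coefficient.

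Section 10.4.1 sets p-values as two-sided, "using a two-sided 0.05 level of significance", and section 10.4.11 says "there will be no adjustment for multiple comparisons".

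Items 2 to 4 add 3-by-3 classification tables, percent agreements, weighted kappa, a Fisher-Freeman-Halton test and intraclass correlations. Item 4 begins "If results show a significant difference between test and retest for DCTclock", says that such a difference would not make DCTclock less reliable than MMSE, and rests sufficiency on ICC and kappa.

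The study schematic has the tests repeated "after one to four weeks without feedback, minimizing learning effects". No mean change between readings, and no value of the fitted line at a typical score, is named in section 10.4.5.

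**The concern.** A practice effect that raises everyone's score by about the same amount keeps the slope at 1. Of the two tests in item 1, only the intercept test can respond. The intercept is an extrapolation to score 0, and where participants score many SDs above 0 its standard error is dominated by the slope's standard error multiplied by the mean score.

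The other score-level statistics do not make up for this:
- A correlation ignores a shift.
- Even an absolute-agreement ICC hardly moves: with r = 0.8 and a 0.2 SD shift it is 0.80/(1 + 0.2²/2) = 0.784.
- The Fisher-Freeman-Halton test, applied to the reading 1 by reading 2 table, assesses association between rows and columns, not equality of the two margins.

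At stake is the comparison of retest behaviour between two instruments on different scales. A test whose sensitivity changes with the position of zero is not a like-for-like basis for it. A shift of this size would matter: if scores are normal with a fixed cut-off and 30% are impaired at reading 1, a 0.2 SD gain gives Φ(−0.524 − 0.2) = 23.4% at reading 2.

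**Working it through.** The protocol states no power or sample size for the test-retest analysis, so there is no figure to reproduce.

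**Inputs from the protocol**
- Two tests, intercept vs 0 and slope vs 1 (section 10.4.5), each two-sided at 0.05 (section 10.4.1) with no multiplicity adjustment (section 10.4.11).
- Number of pairs n: 400 as an upper figure (section 10.4.3: "Approximately 500 participants will be enrolled to obtain 400 evaluable participants"). Section 5.4.2 says "Participants who withdraw or do not complete the second visit will not be replaced" and gives no loss rate, so 300 was also run as an assumption.

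**Assumptions (not in the protocol)**
- Retest correlation r of 0.7 to 0.9.
- A constant shift of 0.1 or 0.2 SD.
- Deming error-variance ratio of 1, because the same instrument is used twice.
- Mean/SD of the score, written m, varied from 0 to 12.

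**Formulas, in SD units**
- SE(slope) = √[(1 − r²)/(n r²)]
- SE(difference) = √[2(1 − r)/n]
- SE(intercept) = √[SE(difference)² + (m × SE(slope))²]
- Power ≈ Φ(shift/SE − 1.96) + Φ(−shift/SE − 1.96)

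**n = 400, r = 0.8, shift 0.2 SD**

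SE(slope) = √[0.36/(400 × 0.64)] = 0.0375. SE(difference) = √(0.4/400) = 0.0316.

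| m | SE(intercept) | shift/SE | Power, formula | Power, simulation | Paired difference |
|---|---|---|---|---|---|
| 0 | 0.032 | 6.32 | 1.00 | 1.00 | 1.00 |
| 2 | 0.081 | 2.46 | 0.69 | 0.69 | 1.00 |
| 5 | 0.190 | 1.05 | 0.18 | 0.19 | 1.00 |
| 9 | 0.339 | 0.59 | 0.09 | 0.11 | 1.00 |

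The simulation used 1,000 replicates per setting with jackknife standard errors. The slope test stayed near 0.05, so counting either test as a detection adds only about 1 to 3 percentage points.

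**Sensitivity**
- *Correlation.* At m = 9 and 0.2 SD, simulated intercept power is 0.095 for r = 0.7 and 0.142 for r = 0.9. At m = 2 and r = 0.9 it is 0.953.
- *Fewer pairs.* With n = 300 and r = 0.8, intercept power is 0.57 (m = 2), 0.16 (m = 5) and 0.09 (m = 9). Paired power is at least 0.999.
- *Smaller shift.* At 0.1 SD and n = 400, paired power is 0.70-0.998 over r = 0.7 to 0.9, so it is not certain to detect every shift.
- *Ceiling.* For an assumed bounded 0-30 integer score from two-group mixes and a 0.5-point shift, intercept power is 0.29-0.43 over three mixes and paired power is 0.999. In the mix with mean 26.4, SD 2.88 and r = 0.82, the intercept has 0.29 and the slope 0.17. Without the ceiling the intercept has 0.10.

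**Consequence for the comparison.** Suppose, for illustration, that one instrument has m = 2 and the other m = 9, with the same 0.2 SD shift and r = 0.8. Simulated power is then 0.69 for the first and 0.11 for the second. Nothing differs between them except where zero lies.

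**The case against.** A reader might infer that the intercept test has almost no power for a practice effect in DCTclock. The documents do not support that. The DCTclock scale is not given and much of the device description is redacted. If mean/SD lies between 0 and 2, intercept power at 0.2 SD and r = 0.8 is 0.69 to 1.00, and at 0 it equals the paired test. A ceiling also raises power, although it stays well short of the paired test. This objection stands and makes the point conditional.

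A reader might also infer that a non-significant intercept will be taken as proof of no change. No section says so. Item 4 deals only with a significant result and discounts it, and sections 10 and 10.4.1 make the comparison with MMSE descriptive. This stands too. The learning-effects remark in the schematic describes the design and does not announce a test.

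The wording might allow a joint test of intercept and slope. A simulated joint Wald test (n = 400, r = 0.8, 0.2 SD) had power 1.00 at mean/SD of 2, 4.7 and 9. However, the protocol writes two separate pairs of hypotheses, which reads more naturally as two tests.

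Finally, the scatter plot, the intercept's confidence interval and the table margins would let an attentive reader see a shift or the imprecision, and the SAP may add summaries. That softens the consequence. It does not change the fact that the protocol itself names the tests to be used, and that their sensitivity depends on scale origin.

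**Conclusion.** The point holds in conditional form. Under the separate-test reading, the formal assessment of systematic score change has power that depends on scale origin: for a 0.2 SD uniform shift with 400 pairs and r = 0.8, about 0.69 at mean/SD 2, 0.20 at about 5 and 0.09-0.11 at 9, against about 1.00 for the paired mean difference. Low power applies where scores lie far from 0, as for an MMSE-like score (about 0.29-0.43 with the assumed ceiling). It is not established for DCTclock.

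The shift, correlation, error ratio and scale positions are all assumptions, because the protocol gives none of them. The practical effect is on the descriptive comparison of DCTclock and MMSE retest behaviour. The primary kappa analysis and the ICC/kappa criterion for sufficient reliability are not affected.

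**What to change.** In section 10.4.5 item 1, add the paired mean difference (reading 2 minus reading 1) with its 95% confidence interval, for DCTclock and for MMSE, and name it as the assessment of systematic change. Limits of agreement are optional.

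Alternatively, keep the Deming regression but subtract the reading 1 mean from both readings before fitting. The intercept then estimates the change at a typical score and has the precision of the m = 0 row. The same constant must be subtracted from both readings; centring each at its own mean would force the intercept to zero.

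Either way, state that a non-significant uncentred intercept is not evidence that no change occurred.

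The cost is a few lines in the protocol and the SAP. No additional data are needed, since both readings are already part of the design.

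### Section 10.4.5 item 3 tests the paired retest table with Fisher-Freeman-Halton, whose null is independence, so ordinary retest agreement would be reported as a difference between readings

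*Protocol*

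**What the plan says.** Section 10.4.5, item 3, takes DCTclock and MMSE separately. It classifies each participant as impaired, indeterminate/intermediate or unimpaired "at each of the two measurements obtained on each participant" and sets out a 3x3 table "with the rows being the second reading status and with columns being the first reading cognitive status". It then specifies: "The Fisher-Freeman-Halton exact test will be used to assess if the cognitive classifications differ between reading 1 and 2". The hypothesis is spelled out: "The null hypothesis is that reading 2 and reading 1 do not differ with respect to cognitive classifications". Section 10.4.1 sets the level for all p-values, "using a two-sided 0.05 level of significance".

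Item 4 anticipates a significant test-retest difference for DCTclock and says this would not mean lower reliability than MMSE. It puts the reliability conclusion elsewhere: "Results showing that DCTclock has similar or better ICC/ kappa than neuropsychological battery variables and MMSE will be considered as sufficient reliability".

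The Schematic of Study Design, step 5, repeats the testing "in the same subjects after one to four weeks without feedback, minimizing learning effects", so a shift between visits is something the design itself has in view.

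**The concern.** The Fisher-Freeman-Halton test conditions on both sets of margins and asks whether rows and columns are associated. On a table of reading 2 by reading 1 in the same people, no association means that the second classification is unrelated to the first, that is, agreement no better than chance. This differs from the null the protocol states, and the test errs in two ways:

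- When classifications are stable, the readings agree, independence fails and the test is significant. The plan would call this a difference.
- When agreement is at chance, the test is non-significant even if the proportions in each category have moved a long way, because margins that are conditioned on carry no information about a shift.

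This is the only p-value planned on the retest classifications, and it is produced for both instruments. It cannot show whether classifications shifted between visits, for example through learning. A report that follows the plan would almost certainly contain a false statement that classifications differed.

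**Working it through.** **The plan's own figure.** The only power figure in the protocol is for the primary kappa test (section 10.4.3: 400 evaluable, true kappa 0.52 against 0.40, one-sided 0.025, at least 80%). With the large-sample standard error of unweighted kappa on a 3x3 table it recomputes to 0.85 to 0.915 over the stated margins, so it is reproduced. None is given for item 3.

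**Inputs.**
- From the protocol: the table, test and null (10.4.5 item 3); two-sided 0.05 (10.4.1); 400 evaluable; impaired and unimpaired each 20% to 42.5%, indeterminate 15% to 60% (10.4.3).
- Assumed, because the protocol does not give them: retest kappa, and the number with both readings (200, 300 or 400).

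**Step 1: the stated null made true.** Let both readings have the same margins m and retest kappa k, with cell probabilities

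p_ij = (1 − k)·m_i·m_j, plus k·m_i on the diagonal.

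The margins are then identical at both visits. The departure from independence is

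Σ(p_ij − m_i·m_j)² / (m_i·m_j) = k²·[Σ(1 − m_i)² + 1 − Σm_i²] = 2k²,

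whatever the margins. The association test on 4 df therefore has non-centrality 2nk². For n = 400 this is 8 at k = 0.10 and 32 at k = 0.20. Against the critical value 9.49, rejection is 60% and 99.8%.

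**Step 2: simulation.** 10,000 tables per setting (margins 0.3/0.4/0.3), with chi-square on 4 df standing in for Fisher-Freeman-Halton. Share of studies declaring a difference when there is none:

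| Retest kappa | n = 400 | n = 300 | n = 200 |
|---|---|---|---|
| 0.10 | 60% | 46% | 31% |
| 0.20 | over 99% | 98% | 89% |
| 0.30 | 100% | 100% | 99.9% |

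At kappa 0 and n = 400 the rate is about 5%. At n = 400, with impaired at 20%, 30% or 42.5%, the figures are 59–60% at kappa 0.10 and 99.5–99.7% at 0.20. Monte Carlo Fisher-Freeman-Halton itself (600 tables, n = 400) gives 3.7%, 59.7%, 99.7% and 100% at kappa 0, 0.10, 0.20 and 0.30, so the stand-in is adequate. Stuart-Maxwell stays at 4–5% at n = 300 and n = 400.

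**Step 3: two constructed tables of 400** (rows reading 2, columns reading 1).
- Table 1: 98/22/0, 22/116/22, 0/22/98. Margins are 120/160/120 at both readings.
- Table 2: 80/2/0, 38/120/2, 2/38/118. Margins move from 120/160/120 to 82/160/158.

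Quadratic weighted kappa is one minus observed over expected mean squared category distance. Observed is 88/400 = 0.22 in both tables (Table 1: 88 adjacent discordances; Table 2: 80 adjacent plus 2 × 4). Expected is 1.2 in both. Kappa is 1 − 0.22/1.2 = 0.82 for each.

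Fisher-Freeman-Halton gives p = 0.0001 for both, the floor with 9,999 permutations (chi-square p about 7e-82 and 3e-92). It cannot tell them apart.

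Stuart-Maxwell for Table 1: the margins are equal, so p = 1.0. For Table 2: the marginal differences in the first two categories are (−38, 0). The variance terms are 82 + 120 − 2·80 = 42 and 160 + 160 − 2·120 = 80, with covariance −(2 + 38) = −40. The statistic is 38²·80 / (42·80 − 40²) = 115,520 / 1,760 = 65.6 on 2 df, p about 6e-15.

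**Step 4: the two extremes.** Perfect agreement (133/134/133 on the diagonal) gives a Fisher-Freeman-Halton p below 10⁻¹⁸⁷, though nobody changed category. Chance agreement with a large shift (30/40/30% to 10/40/50%, n = 400) gives Fisher-Freeman-Halton p = 1.0 and Stuart-Maxwell p about 8e-13.

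**The case against.** The best case on the other side is that little depends on this p-value.

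- **Item 4 disarms it.** It says a significant difference does not imply poorer reliability, and rests the conclusion on ICC and kappa. This stands and limits the consequence. But item 4 still reads significance as a test-retest difference, which this test cannot establish.
- **Shift is examined elsewhere.** Item 1 tests the Deming intercept against 0 and slope against 1 on the scores. Item 2 gives percent agreement by category with Wilson intervals: in the constructed tables impaired agreement is 98/120 = 81.7% against 80/120 = 66.7%, and unimpaired 98/120 = 81.7% against 118/120 = 98.3%. The printed margins would also show the shift. All true: a careful reader would see it. But item 1 concerns scores, item 2 has no test of shift, and the one p-value on classifications remains misleading.
- **Significance is not automatic.** At kappa 0.10 the test misses the association in about 40% of studies at n = 400. Near-certain rejection begins at about 0.2 with n = 400 and about 0.3 with n = 200. That limit is right and is part of the conclusion.
- **A stacked 2x3 table may have been meant** (reading by category). This would compare the margins, but it is not the table drawn. It also ignores pairing: its rejection rate under equal margins falls from about 5% towards 0% as kappa rises.
- **Other paired tests would serve.** Bowker's test of symmetry is a fair alternative, as is dropping the test and keeping kappa with its interval. Marginal homogeneity is the closest match to a question about shift.

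An unseen SAP does not resolve the matter, because the protocol itself fixes the table, the test and the null.

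**Conclusion.** The concern holds. Item 3 names a test whose null differs from the one stated beside it. With 400 paired readings and no true shift, it would declare a difference in about 60% of studies at retest kappa 0.10 and in over 99% from 0.20. With 200, near-certainty is reached at about 0.30. The figures assume equal margins at both readings, the cell structure in step 1, and ranges for retest kappa and sample size that the protocol does not give. The qualitative point needs none of these.

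The error is contained: one secondary p-value for each of DCTclock and MMSE, and the sentence reported from it. It should be fixed, but the primary endpoint, the sample size and the ICC/kappa reliability criterion are not affected.

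**What to change.** Replace the two sentences after the table in section 10.4.5, item 3, with:

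> For each of DCTclock and MMSE, the Stuart-Maxwell test of marginal homogeneity (permutation version, swapping the two readings within participant, if discordant cells are sparse) will compare cognitive classifications at readings 1 and 2. The null hypothesis is that the marginal proportions impaired, indeterminate/intermediate and unimpaired are equal at the two readings. This tests systematic shift, not reliability.

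Keep the planned quadratic weighted kappa with its 95% confidence interval as the measure of agreement. Item 4's remark about a significant test-retest difference then refers to a test that can show one, and any SAP should carry the same wording. The cost is two sentences and a standard R function, with no new data and no change to sample size.
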